### 6.6.1.2. Sensitivity Analysis

To assess the robustness of the results to the MAR assumption, additional sensitivity analyses using the tipping point approach will be used to assess how extreme and detrimental outcomes among patients with missing data must be to overwhelm the treatment effect attained in those patients who had complete data. In these analyses, the same basic analytic model will be used as in the primary analysis, but the MI approach will be expanded to allow for varying impact of missing data by incorporating a shift parameter in the imputation model. The range of values for the shift parameter will explore the varying missing data assumptions, from MAR to missing not at random, including the scenario where imputation model is completely based on the control group (ie, control-based imputation).

For the sparsentan-treated patients, the post-discontinuation imputed values from MI step 2 will be made worse by subtracting a delta defined as  $k$  times the treatment differences (means or slopes) obtained for the post-discontinuation visits obtained from the specified mixed model analysis (ie, the analytic model) of the endpoint. No adjustment from the MAR assumption will be implemented for the irbesartan-treated patients (ie,  $k = 0\%$ ).

1. Generate worse-case scenarios with varying values of  $k$  (eg, 100%, 120%, 140%...200%...) until the significance of the prespecified analysis assuming MAR is overturned (eg, from  $p\text{-value} < 0.05$  to  $p\text{-value} \geq 0.05$ ). The worsening by  $k$  times the treatment differences is applied to all the post-discontinuation imputed values for each set of “complete” data from MI step 3. As an example, if a sparsentan patient had 2 post-discontinuation visits imputed, the values of both of these 2 imputed visits would be made worse by subtracting  $k$  times the sparsentan versus irbesartan treatment differences at these 2 visits.
2. Note that when  $k = 0\%$ , this approach produces an analysis that is consistent with MAR and is equivalent to the primary analysis with MI.
3. When  $k = 100\%$ , this approach produces an analysis that is equivalent to “jump to reference,” since the whole treatment differences were subtracted out from the imputations based on the trend of the control group.
4. When  $k > 100\%$ , the analysis reflects a “worse-than-control” specification.

### 6.6.1.3. Local Laboratories

The primary analyses will use central laboratory data only. As a sensitivity analysis, local laboratory data will be included with central laboratory data.

### 6.6.2. Missing Adverse Event or Concomitant Medication Onset Date

Adverse events (AEs) and concomitant medications with incomplete onset dates will be assumed to have started during the study in accordance with the following prioritized list of assumptions:

1. Missing year: event or medication assumed to have the same year as first dose of study medication or year of end date, whichever is earlier.
2. Missing month: event or medication assumed to have started during the study if the year is the same or later than the year of the first dose of study medication. Event or medication assumed to have started at the same month of the first dose of study

medication or same month as end date (if year of end date  $\leq$  year of event), whichever is earlier.

3. Missing day: event or medication assumed to have the same day as first dose of study medication if the year and month of onset are the same as year and month of first dose of study medication or the same day as end date, whichever is earlier. Otherwise, the day is assumed to be the first of the month.

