### 7.1.2. Exclusion Criteria for the Double-blind Period

A patient who meets any of the following criteria will be excluded from this study:

1. The patient has IgAN secondary to another condition (eg, systemic lupus erythematosus, liver cirrhosis) or Henoch-Schonlein purpura.
2. The patient has cellular glomerular crescents present in >25% of glomeruli on renal biopsy within 6 months prior to screening.
3. The patient has a CKD in addition to IgAN.
4. The patient has undergone any organ transplantation, with the exception of corneal transplants.
5. The patient requires any of the prohibited concomitant medications (see [Section 15.2.1](#)).
6. The patient has been taking any systemic immunosuppressive medications (including corticosteroids) for >2 weeks within 3 months prior to screening.
7. The patient has a documented history of heart failure (New York Heart Association Class II-IV) and/or previous hospitalization for heart failure or unexplained dyspnea, orthopnea, paroxysmal nocturnal dyspnea, ascites, and/or peripheral edema.
8. The patient has clinically significant cerebrovascular disease (transient ischemic attack or stroke) and/or coronary artery disease (hospitalization for myocardial infarction or unstable angina, new onset of angina with positive functional tests, coronary angiogram revealing stenosis, or a coronary revascularization procedure) within 6 months prior to screening.
9. The patient has jaundice, hepatitis, or known hepatobiliary disease (excluding asymptomatic cholelithiasis), or alanine aminotransferase (ALT) and/or aspartate aminotransferase (AST) >2 times the upper limit of the normal range at screening.
10. The patient has a history of malignancy other than adequately treated basal cell or squamous cell skin cancer or cervical carcinoma within the past 2 years.
11. The patient has a screening hematocrit value <27% (0.27 Volume/Volume) or hemoglobin value <9 g/dL (90 g/L).
12. The patient has a screening potassium value of >5.5 mEq/L (5.5 mmol/L).
13. The patient has a history of alcohol or illicit drug use disorder (as defined in the Diagnostic and Statistical Manual of Mental Disorders, Fifth Edition).

14. The patient has a history of serious side effect or allergic response to any AngII antagonist or ERA, including sparsentan or irbesartan, or has a hypersensitivity to any of the excipients in the study medications.

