#### **8.4. Prior and Concomitant Medications and Therapeutic Procedures**

For enrolled patients, prior and concomitant medications and therapies will be collected from the 3 months prior to screening through the patient's final study visit. In addition, a comprehensive history of medications previously used for treatment of IgAN, including systemic corticosteroids or other systemic immunotherapeutic agents, will be collected. Prohibited concomitant medications and other concomitant medication considerations during study participation are outlined in [Section 15.2.1](#).

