### **6.6.3. Missing Adverse Event or Concomitant Medication End Date**

If the entire end date is unknown and the event or concomitant medication is not considered ongoing at the end of study or follow-up, the event or medication will be assumed to have ended on the last date of contact for the patient.

If only the day of end date is unknown, the day will be assumed to be the last of the month or the last date of contact for the patient, whichever is earlier.

If both the day and month of end date are unknown, the event or medication will be assumed to have ended on the last day of the year or the last date of contact for the patient, whichever is earlier.

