### 8.5.2. Sensitivity Analyses of the Primary Efficacy Results

Robustness of the primary analysis of the primary efficacy endpoint due to missing data or premature treatment discontinuations (including the impact of COVID-19) will be explored by the following sensitivity analyses:

- Tipping point approach of the MI analysis as described in [Section 6.6.1.2](#)
- MMRM analysis using observed data (with no imputation of missing data)
- MMRM analysis using completers only (patients with non-missing UP/C values at Week 36 (212 to 295 days))

- MMRM analysis using observed data (with no imputation of missing data) during the double-blind period including after premature treatment discontinuation (treatment policy estimand). Additional analysis exploring potential intercurrent events that could impact the primary analysis (eg, premature discontinuation of study drug, use of immunosuppressive agents, loss to follow-up, withdrawal of consent, need for RRT, or death) may be performed to examine their impact.

To assess the impact of changes in systemic immunosuppressive medications, the primary efficacy analysis will be repeated by excluding assessments after initiation of renal indication of systemic immunosuppressive medication in the blinded treatment period.

To assess the potential impact of patient evaluability and major protocol deviations, the primary efficacy analysis will be repeated using the PP Analysis Set.

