#### **8.7.5. Analyses of Events Rates**

The following efficacy endpoints, considered event rate endpoints, will be analyzed using a negative binomial regression model, via PROC GENMOD in SAS:

- Number of systemic immunosuppressive medications over the treatment period
- Number of days treated with systemic immunosuppressive medications
- Number of hospitalizations (for any reason and for reasons related to the kidney)

Specifically, the model will compare treatment groups, adjusted for the randomization stratification factors, and will include the natural log transformation of duration of exposure as an offset term. Estimated event rates will be extracted from the model for each treatment. The treatment effect will be presented as the ratio of event rates, along with the associated 95% CI and 2-sided p-value.

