### 10.3. Prior and New Concomitant Medications and Procedures

Prior and concomitant medications and procedures will be collected from 3 months prior to Screening through the patient's final study visit. In addition, a comprehensive history of medications previously used for treatment of IgAN, including systemic corticosteroids or other systemic immunotherapeutic agents, will be collected. For medications, verbatim terms on eCRFs will be mapped to Anatomical Therapeutic Chemical (ATC) class and preferred name using the World Health Organization (WHO) Drug Dictionary Enhanced. For procedures, verbatim terms will be mapped to PTs and SOC using MedDRA.

Pretreatment medications are those medications with start and stop dates prior to the initial dose of study medication. Prior concomitant medications are those medications started prior to and continued after the initial dose of study medication. New concomitant medications are those medications that were started on or after the initial dose of study medication. If it cannot be determined whether the medication was a new concomitant medication due to a partial start or stop date or if the medication is taken on the same date as the initial dose of study medication, then it will be counted as a new concomitant medication.

Similarly, prior procedures are those procedures with a start date prior to initial dose of study medication. Concomitant procedures are those procedures that were started after the initial dose of study medication.

Select pretreatment medications, including ACEIs, aldosterone blockers, aliskiren, ARBs, corticosteroids, immunosuppressive medications, diuretics, and all antihypertensives, will be summarized for each treatment group by WHO ATC level 2, WHO ATC level 4, and preferred name. All other pretreatment medications will be listed only.

Prior and new concomitant medications will be summarized separately for each treatment group by WHO ATC level 2, WHO ATC level 4, and preferred name. These summaries will present the number and percentage of patients using each medication. Patients may have more than one medication per ATC level and preferred name. At each level of patient summarization, a patient

is counted once if he/she reported one or more medications at that level. Each summary will be ordered by descending order of incidence of ATC level and preferred name within each ATC level.

Prior and concomitant procedures will be summarized for each treatment group by SOC and PT.

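### Medications with no usable onset date and no recorded stop before Day 1 are dated to Day 1 and counted as new, and year-only onsets in later years can be dated up to 334 days late (335 in a leap year)

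*SAP*

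**What the plan says.** SAP 6.6.2 is written expressly for adverse events and concomitant medications together, and presumes that incompletely dated items began on study. A missing year is filled by this rule: "event or medication assumed to have the same year as first dose of study medication or year of end date, whichever is earlier". For a missing month: "Event or medication assumed to have started at the same month of the first dose", or in the end-date month if that is earlier and the end year is not after the onset year. A missing day takes the first-dose day if year and month match the first dose, again limited by the end date; otherwise it becomes the first of the month.

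SAP 6.6.3 handles stops. If the whole end date is unknown and the item is not ongoing, "the event or medication will be assumed to have ended on the last date of contact for the patient". A stop known only by year becomes the last day of that year, or last contact if earlier.

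SAP 10.3 treats a start on or after first dose as new. If a partial date leaves the status undetermined, "then it will be counted as a new concomitant medication".

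Pre-study drugs are collected by design. Under Protocol 8.4, beyond the three-month look-back, "a comprehensive history of medications previously used for treatment of IgAN, including systemic corticosteroids or other systemic immunotherapeutic agents, will be collected".

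**The concern.** For an adverse event, defaulting to Day 1 is cautious, because it keeps the event in the treatment-emergent tables. For a medication it can turn pre-study use into on-study use, and the 10.3 default leans the same way.

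The dates feed several analyses:

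- time to immunosuppressant initiation (SAP 8.7.4.1);
- immunosuppressant use by 12-week period (8.7.4);
- the count "Number of days treated with systemic immunosuppressive medications" (8.7.5);
- the subgroup with concomitant but no baseline immunosuppressant use, and the baseline antihypertensive subgroup (8.3);
- the sensitivity analyses of UP/C (8.5.2) and eGFR slope (8.6.3), the former run by "excluding assessments after initiation of renal indication of systemic immunosuppressive medication in the blinded treatment period".

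A false Day 1 initiation with a renal indication would remove all of that patient's post-baseline values from those sensitivity analyses. An onset dated too late does the opposite and leaves in values that should have been dropped.

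**Working it through.** The SAP gives no figure to reproduce, so the rules were applied step by step.

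**1. Which records reach Day 1.** Take first dose 15 June 2020 and apply the year, month and day rules in turn.

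| Onset recorded | Stop recorded | Imputed start | Result |
|---|---|---|---|
| none | none, or ongoing | 15 Jun 2020 | Day 1, new |
| none | 20 Mar 2021 | 15 Jun 2020 | Day 1, new |
| 2020 only | none | 15 Jun 2020 | Day 1, new |
| none | 14 Jun 2020 | 14 Jun 2020 | starts before Day 1 |
| none | 10 Feb 2020 | 1 Feb 2020 | starts before Day 1 |
| none | 10 Oct 2019 | 1 Jun 2019 | starts before Day 1 |
| 2019 only | none | 1 Jun 2019 | starts before Day 1 |

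In 200,000 randomly drawn cases with a fully known stop before Day 1, none was dated to Day 1 or later. The end-date limit works when the stop is known.

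**2. A stop known only as the first-dose year.** First dose 15 November 2019, start unknown, stop 2019.

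- End (6.6.3): 31 December 2019.
- Year: earlier of 2019 and 2019 = 2019.
- Month: earlier of November and December = November.
- Day: earlier of 15 and 31 = 15.

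The start is 15 November 2019, which is Day 1, even if the course really stopped in March.

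**3. Size per record.** An immunosuppressant course with both dates missing, not ongoing, runs from Day 1 to last contact. By the target days in SAP Table 1, that is 771 days to Week 110 or 799 days to Week 114.

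**4. Plausibility at entry.** Exclusion criterion 6 reads: "The patient has been taking any systemic immunosuppressive medications (including corticosteroids) for >2 weeks within 3 months prior to screening". It does not rule out a short course, but it makes sustained use running through entry implausible.

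**5. Later-year onsets.** With only a later year known, the month rule copies the first-dose month and the day rule gives the 1st. Maximum lateness is the gap from 1 January:

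- January first dose: 0 days
- June: 151
- September: 243
- December: 365 − 31 = 334 (366 − 31 = 335 in a leap year)

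An end date earlier in that year caps this: with a December first dose and a stop on 10 April 2021, the start is 1 April 2021.

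Averaged over equally likely first-dose months, the imputed date is 1,998/12 = 166.5 days after 1 January. If true onsets are uniform over a 365-day year (an assumption), they average 182 days after 1 January. The rule is then 166.5 − 182 = 15.5 days early on average, and late in 166.5/365 = 46% of cases.

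**6. A wording ambiguity.** The day rule does not say whether full dates or only days of the month are compared. With first dose 15 June 2020 and stop 10 March 2021, the first reading gives 15 June 2020 and the second gives 10 June 2020.

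**The case against.** A reader might infer that every undated pre-study drug becomes new on-study use. The text does not support that. The end-date limit keeps any drug with a known stop before Day 1 in the pre-study period, including ACEI/ARB therapy last taken the day before randomization. An onset year before the first-dose year also keeps the start pre-study. Nor are these adverse event rules carried over by accident: the section names both.

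It can be argued that IgAN treatment history sits on separate forms (SAP 7.5) and never enters this derivation. The forms are not visible, but SAP 7.4 identifies pretreatment immunosuppressants by reviewing concomitant medication records, so the objection fails on the text.

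The medical review in SAP 8.7 might catch an obviously historical course. However, it is described as reviewing medications and their indications to establish renal use. It has no stated authority over dates, and it does not reach antihypertensives or the all-indication immunosuppressant analyses.

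Two further points stand. The 166.5-day figure is distance from 1 January, not expected lateness. And no directional bias between arms is shown: the same rules apply to both blinded arms.

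**Conclusion.** The defect is real but limited. It covers medications with onset wholly missing, or known only as the first-dose year, and no stop that resolves to before Day 1. In practice these are:

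- continuing non-RAAS antihypertensives with unknown start;
- immunosuppressant courses with both dates missing;
- courses with unknown start and a stop known only as the first-dose year.

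One such antihypertensive record can move a patient to the no-baseline-use group, if that subgroup follows the 10.3 categories and no other qualifying drug is recorded.

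The later-year month rule is a separate fault: up to 334 days late (335 in a leap year), needing a December first dose and no earlier end date. It can leave post-initiation values in the sensitivity analyses. For patients who discontinue, it can also move an adverse event beyond the 30-day on-treatment window of SAP 10.1.3. The partial-date safeguard in SAP 10.1 protects treatment-emergent status only.

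The primary and key secondary analyses do not use these dates. The documents give no frequency. If 1% to 3% of 190 patients per arm (380/2) had such a record, an assumption only, that would be about 2 to 6 patients per arm. The stated rules should be corrected, but the main efficacy conclusions do not depend on it.

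**What to change.** Amend SAP 6.6.2, 6.6.3 and 10.3 together; changing 6.6.2 alone leaves the 10.3 default in force.

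- (a) A medication recorded as prior IgAN treatment, or as stopped before first dose, is pretreatment, with imputed dates capped at Day -1.
- (b) A medication recorded at screening or baseline as ongoing, with unknown start, is prior concomitant, and baseline use is Yes.
- (c) Keep the Day 1 default for adverse events and for medications not recorded as prior.
- (d) Copy the first-dose month only when the onset year equals the first-dose year. Otherwise use January, the earliest possible month, in line with the day rule's existing use of the first of the month.
- (e) State that full dates are compared in the day rule.

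The cost is SAP wording and a few lines of derivation code before database lock. No new data are needed if the case report forms already mark medications as prior or ongoing, which the documents do not show.

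There are two downsides. A medication misrecorded as prior is classed as prior. And January dating is conservative rather than accurate: under the uniform assumption it is 182 days early on average, with mean absolute error 182 days against 122 for the current rule, so some valid values may be dropped from the sensitivity analyses.

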### **6.6.3. Missing Adverse Event or Concomitant Medication End Date**

If the entire end date is unknown and the event or concomitant medication is not considered ongoing at the end of study or follow-up, the event or medication will be assumed to have ended on the last date of contact for the patient.

If only the day of end date is unknown, the day will be assumed to be the last of the month or the last date of contact for the patient, whichever is earlier.

If both the day and month of end date are unknown, the event or medication will be assumed to have ended on the last day of the year or the last date of contact for the patient, whichever is earlier.

### **6.6.4. Missing Adverse Event Severity or Relationship**

An event with missing severity will be considered severe. An event with missing relationship will be considered related to study medication.

## **7. STUDY POPULATION**

### **7.1. Patient Disposition**

Patient disposition will be tabulated by treatment group and overall and will include the number of patients who screened, failed Screening, enrolled/randomized, received study medication, completed double-blind treatment, discontinued study medication (including reasons), completed the double-blind period, and discontinued the study during the double-blind period (including reasons). At the primary analysis, the number of patients who enrolled in the OLE period, discontinued sparsentan in the OLE period, and discontinued the study during the OLE period (including reasons for treatment discontinuation) will also be tabulated.

The number and percentage of patients in each analysis set will be summarized.

Patient enrollment by study site and country will be tabulated by treatment group and overall.

A by-patient listing of inclusion into analysis sets and study completion information including reason for study drug discontinuation or early withdrawal from study, if applicable, will be presented.

### **7.2. Screen Failures**

The reason for screen failures will be summarized by region or site, as appropriate.

### **7.3. Protocol Deviations**

Protocol deviations for missed visits, missed assessments, out-of-window visits or assessments, and violations of inclusion/exclusion criteria (where possible) will be determined based on available data. All other protocol deviations will be collected by the clinical research associates.

Protocol deviations that could potentially affect the efficacy or safety conclusions of the study will be identified, and the assessment of determination of evaluable patients for analysis populations (PPPA, PPFA and PK Analysis Set) will be performed and approved by the Study Statistician, Medical Monitor, and Clinical Study Manager prior to database lock and unblinding of individual patient treatment information.

Evaluability of patients will be based on the following:

- Compliance of study entry criteria (inclusion and exclusion)
- Correct stratification at randomization
- Received the randomized treatment
- Adequate study medication exposure (no extended dosing interruptions)
- Adequate treatment compliance based on prescribed dose level (within 80% to 120%)
- No prohibited concomitant medications or therapies during the study
- No accidental or intentional unblinding at the investigational site

- No other major protocol deviations that may affect efficacy or safety conclusions, may include the following:
  - Non-withdrawal although at least 1 withdrawal criterion was met
  - Extensive visit window violations
  - Extensive missing visits
  - Nonadherence to study procedures
  - Inadequate handling of study medication

Major protocol deviations will be summarized by deviation category (overall and due to coronavirus disease 2019 [COVID-19]) and presented in a by-patient data listing.

